5.4.1.2 Fitting and Use of Hearing Aids

Preoperatively, subjects will undergo candidacy testing using their own hearing aid devices. If a candidate does not own hearing aids, testing using loaner hearing aid devices may be provided by the candidate's hearing health provider.

Note: The speech perception criterion for enrollment into the study must be met with appropriately fit hearing aids, (both for the ear to be implanted as well as the non-implant ear), even if amplification proves to provide no measurable benefit over natural acoustic hearing for the particular subject.

To ensure standardization of hearing aid fitting, it is required that hearing aid settings for target and gain are set and verified. Real-ear measures are to be utilized to verify that the slope of the frequency response is within 5 dB per octave of the target slope.

During the fitting process, optimization of the response slope will be the priority for those frequencies where thresholds correspond to aidable hearing. Taking a conservative approach, aidable hearing will be defined by hearing thresholds up to 90 dB HL for this study.

It is recognized that prescriptive methods are based on average requirements, and that individuals may find deviations from target values optimal for sound loudness, quality, or clarity. For example, individual adjustments required to relieve occlusion effects will be permitted.

If the subject does not use hearing aids on a daily basis, does not own hearing aids, or uses hearing aids that are identified as inappropriately fit or poor functioning, the subject will undergo a hearing aid trial and/or readjustment period. The hearing aid trial period will be for a minimum of 30 days or longer as recommended by their study audiologist. At the end of the trial period, aided word recognition testing will be assessed to confirm that candidacy criteria are met.

Subjects will need to be willing to use bimodal stimulation (i.e. a cochlear implant on one ear and a hearing aid on the contralateral ear) through at least 12-months postactivation.

5.4.1.3 Candidacy Assessment

- Air conduction thresholds at 125, 250, 500, 750, 1000, 1500, 2000, 3000, 4000, 6000, 8000 Hz;
 - Unilateral each ear

- Bone conduction thresholds at 125⁵, 250, 500, 750, 1000, 1500, 2000, 4000 Hz;
 - Unilateral each ear

Note: Clinician will need to confirm the subject's response to any pure tone stimulus presented at 125 and 250 Hz as auditory "heard" versus vibrotactile "felt" and record the response accordingly.

- Aided thresholds at 125, 250, 500, 750, 1000, 1500, 2000, 3000, 4000⁶ Hz;
 - Unilateral each ear with contralateral ear plugged
- Tympanometry in each ear
- CNC Word Test Two lists at 60 dB(A) in each of the following conditions:
 - Unilateral aided each ear with contralateral ear plugged

5.4.1.4 Hearing History and Counseling

Information regarding subject hearing-history (e.g., etiology, onset of hearing loss, duration of severe-to-profound hearing loss, amplification use) will be obtained and reported on the respective case-report form. In addition, patients will be carefully and extensively counseled to ensure that their expectations from cochlear implantation are reasonable and appropriate (as determined by the Investigator).

5.4.1.5 **Candidacy Determination**

Once the candidacy evaluation is completed the Investigator is required to submit the candidacy CRFs for review by the Sponsor's study manager, or designee. The data will be reviewed and candidacy assessed by the study manager.

5.4.2 Preoperative Baseline Evaluation

Once candidacy has been established, the following additional testing will be administered to each subject:

5.4.2.1 **Speech Perception Testing**

- CNC Word Test Two lists at 60 dB(A)
 - Bilateral Aided
- S₀N₀ AzBio Sentences in Noise One list at 60dB(A) with a +5 dB SNR in each of the following conditions
 - Unilateral Aided, ear to be implanted with contralateral ear plugged
 - Bilateral Aided

-

⁵ Bone conduction measures at 125 Hz are optional based on potential audiometric equipment limitations.

⁶ Many audiometers are not calibrated for testing at 6000 and 8000 Hz.

5.4.2.2 Questionnaire/Assessment

- Abbreviated Profile of Hearing Aid Benefit (APHAB)
- Speech Spatial and Qualities of Hearing Scale 12 (SSQ12)

Note: The Surgical Procedure must be completed within 3 months of the Candidacy Evaluation. If the interval exceeds 3 months, candidacy needs to be re-confirmed by repeating aided CNC word recognition test measures in quiet for each ear. If a patient experiences a 10% or greater decrement in their word recognition scores, audiometric thresholds must be re-assessed to confirm continued candidacy and the Preoperative Baseline Evaluation must be repeated. Scores from the most recent test session will be used for analysis. If a patient experiences less than 10% decrement in CNC word recognition, the evaluation does not need to be repeated and scores from the initial candidacy/ baseline assessment can be utilized. Any changes observed will need to be reviewed in consultation with the Sponsor prior to surgery occurring.

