4.1 Inclusion Criteria

- 1. Eighteen years of age or older at the time of implantation
- 2. Sensorineural hearing loss with the following requirements: a pure tone threshold less (better) than or equal to 60 dB HL at 500 Hz, less than (better) or equal to 80 dB HL at 1500 Hz, and high frequency severe to profound (a threshold average of 2000, 3000, & 4000 Hz) of > 60dB HL.
- 3. Minimum of 30 days experience with appropriately fit bilateral amplification, fit as described in the *Fitting and Use of Hearing Aids* section below
- 4. Aided monosyllabic word score (e.g., CNC Word Test) (mean of two lists) between 20% and 60%, inclusive (i.e., $20\% \le \text{score} \le 60\%$), in the ear to be implanted
- Aided monosyllabic word score (e.g., CNC Word Test) (mean of two lists) in the contralateral ear equal to, or better than, the ear to be implanted but not more than 80%
- 6. Willingness to use bimodal stimulation (i.e., a cochlear implant on one ear and a hearing aid on the contralateral ear) through 12-months postactivation
- 7. Ability to complete the required test materials.

4.2 Exclusion Criteria:

- Individuals aged greater than 75 years
- 2. Duration of severe to profound hearing loss (above 2kHz) greater than 20 years
- 3. Medical or psychological conditions that contraindicate undergoing surgery as determined by the Investigator
- 4. Ossification or any other cochlear anomaly that might prevent complete insertion of the electrode array
- 5. Conductive overlay of 15 dB or greater at two or more frequencies, in the range 500 to 1000 Hz
- 6. Deafness due to lesions of the acoustic nerve or central auditory pathway
- 7. Active middle-ear infection or tympanic membrane perforation in the presence of active middle ear disease
- Unrealistic expectations on the part of the subject, regarding the possible benefits, risks, and limitations that are inherent to the surgical procedure(s) and prosthetic devices as determined by the Investigator
- 9. Unwillingness or inability of the candidate to comply with all investigational requirements as determined by the Investigator

10. Additional handicaps that would prevent or restrict participation in the audiological evaluations as determined by the Investigator.

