5.4.1 Preoperative Candidacy Evaluation

5.4.1.1 **Informed Consent**

A preoperative interview (as part of the informed consent process) will be conducted by the surgeon and/or audiologist to inform the candidate about all aspects of implantation with a cochlear implant, study expectations, surgical procedure, as well as the evaluation schedule. The risks of surgery shall be explained to the subject as outlined in the Informed Consent Form. These include the risks associated with general anesthesia, as well as other risks such as loss of residual hearing, facial paralysis, dizziness, meningitis, postoperative discomfort, and flap complications. The potential limitations and advantages of cochlear implantation shall also be explained.

After reviewing the Informed Consent Form, the candidate will be given the opportunity to review and ask questions about the Informed Consent Form and/or the study prior to signing the Informed Consent Form. The candidate will be offered the opportunity to take the form home to discuss with family members should they choose to do so. If

³ May be a hardcopy or electronic CRF (eCRF), depending on EDC accessibility at the study site.

⁴ If it is more than 90 days past the date of the Candidacy Evaluation, candidacy needs to be re-confirmed by repeating aided CNC word recognition test measures. If a patient experiences a 10% or greater decrement in their word recognition scores, audiometric thresholds must be re-assessed to confirm continued candidacy and the Preoperative Baseline Evaluation must be repeated. Scores from the most recent test session will be used for analysis. If a patient experiences less than 10% decrement in CNC word recognition, the evaluation does not need to be repeated and scores from the initial candidacy/ baseline assessment can be utilized. Any changes observed will need to be reviewed in consultation with the Sponsor prior to surgery occurring.

they sign the Informed Consent Form, the candidate will then be given a copy of the signed Informed Consent Form to take home.

A candidate is not considered enrolled until a properly executed Informed Consent Form has been obtained and, along with the results of the preoperative candidacy evaluation, reviewed and approved by Cochlear representative.

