5.7 Summary of Data Collection Visits

Test	Condition	Preoperative			Postoperative			
		Candidacy	Baseline	Surgery	Activation	3 Month	6 Month	12 Month
Informed Consent		Х						
Air Conduction Audiogram	Unilateral Each Ear	X			X	X	X	Х
Bone Conduction Audiogram	Unilateral Each Ear	х			Х	х	х	х
Aided Audiogram	Hearing Aid Unilateral Each Ear	X						
	Best Unilateral Implanted Ear) `		Х	If >10dB ▲ unaided	If >10dB ▲ unaided	If >10dB ▲ unaided
Tympanometry	Unilateral Each Ear	X			Х	Х	Х	Х
CNC words	Hearing Aid Unilateral Each Ear	х						
	Hearing Aids Bilateral		Х					
	Best Unilateral Implanted Ear					х	х	х
	Best Bilateral					X	Х	Х
	Electric Alone					X	Х	X
AzBio Sentences In Noise	Hearing Aid Ear to be Implanted		х					
	Hearing Aids Bilateral		Х					
	Best Unilateral					X	Х	Х

Cochlear						
	Implanted Ear					
	Best Bilateral			X	Х	X
	Electric Alone			X	Х	X
Surgical Questionnaire			Х			
Questionnaire						
APHAB		X		X	Х	Х
SSQ 12		X		X	Х	Х

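### When surgery is late, candidacy is re-confirmed by aided CNC alone: unless CNC falls by 10% or more no audiogram is repeated, and the CNC pass rule is not stated

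*Protocol*

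**What the plan says.** Three inclusion criteria in Section 4.1 matter here.

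- Criterion 2 sets unaided threshold limits: "a pure tone threshold less (better) than or equal to 60 dB HL at 500 Hz", at most 80 dB HL at 1500 Hz, and an average above 60 dB HL over 2000, 3000 and 4000 Hz.
- Criterion 4 sets the aided CNC range for the ear to be implanted: "mean of two lists) between 20% and 60%, inclusive".
- Criterion 5 requires the other ear to score at least as well as the implant ear, and no more than 80%.

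Section 5.4 defines the candidacy evaluation as the check against the inclusion and exclusion criteria. It requires candidacy to be re-assessed if more than 90 days pass before surgery.

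The procedure for that case appears twice. Footnote 4 says "candidacy needs to be re-confirmed by repeating aided CNC word recognition test measures"; the Note in Section 5.4.2.2 says "candidacy needs to be re-confirmed by repeating aided CNC word recognition test measures in quiet for each ear". Both then split on the size of the fall. For the larger fall: "If a patient experiences a 10% or greater decrement in their word recognition scores, audiometric thresholds must be re-assessed to confirm continued candidacy", and the baseline evaluation is repeated. For the smaller: "If a patient experiences less than 10% decrement in CNC word recognition, the evaluation does not need to be repeated", and the initial candidacy or baseline scores may be used. Any observed change is to be reviewed with the sponsor before surgery.

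In the Section 5.7 schedule, the only pre-operative entry for "Air Conduction Audiogram" is at candidacy. The baseline evaluation in Section 5.4.2 contains no audiogram.

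**The concern.** Re-assessing candidacy suggests that all time-varying entry criteria are looked at again, but the procedure repeats one test, aided CNC. Criterion 2 concerns unaided thresholds, which an aided word score does not measure. They are looked at again only if CNC has dropped by 10% or more.

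Two things are at stake. The first is eligibility at the time of surgery, for an implant whose effect on residual hearing can be permanent (Section 10.0). The second is the reading of efficacy objective 1 (Section 8.3.1), which asks whether measurable low-frequency thresholds can be maintained. If the last pre-operative audiogram is old, loss that occurred while waiting for surgery cannot be separated directly from loss caused by implantation. With at most 10 subjects (Section 4.0), one subject read wrongly is at least 1/10 = 10% of the data.

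A secondary problem is that the smaller-fall branch does not say what happens when the retest lies outside the CNC limits, and its 10% is not defined.

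**Working it through.** The protocol gives no figure to reproduce, since Section 8.1 makes no sample size estimate. The check is a reading of the branches, followed by an illustrative calculation for CNC.

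**1. What is rechecked when surgery is late**

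| Retest result | CNC limits (criteria 4, 5) | Thresholds (criterion 2) |
|---|---|---|
| Fall of 10% or more | retested; pass rule not stated | re-assessed |
| Fall below 10% | retested; pass rule not stated, initial scores may stand | not measured |
| Rise | no branch of its own | not measured |

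The last column does not depend on how re-confirmed is read. A 500 Hz threshold of 60 dB HL at candidacy that worsens by 5 dB becomes 65 dB HL and fails criterion 2. With stable CNC, nobody would see it. The documents give no rate of threshold drift, so this part cannot be sized.

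**2. Which CNC retests leave 20-60% without reaching the trigger**

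Two lists of 50 words (Section 5.3.2) give 100 words, so scores move in 1% steps. Let S be the first score and R the retest, in the implant ear.

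- Low side, 10% as points: R ≤ 19 and S − R < 10 give S ≤ 28, so first scores of 20-28% are exposed.
- Low side, 10% as a relative fall: (S − R)/S < 0.10 with R = 19 gives S < 19/0.9 = 21.1, so only 20% and 21% are exposed.
- High side: a rise is never a decrement, so any first score of 20-60% can retest above 60%.

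For example, 58% to 66% is a rise of 8 points and never triggers. A change from 24% to 16% is a fall of 8 points: below the trigger if 10% means points, above it if relative (8/24 = 33%).

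**3. How often this could happen by chance**

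Assume binomial scoring of 100 words with true ability unchanged at the first score.

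| First score | P(R < 20 and fall < 10 points) | P(R > 60) |
|---|---|---|
| 20% | 45% | 0% |
| 22% | 27% | 0% |
| 25% | 9% | 0% |
| 28% | 1% | 0% |
| 55% | 0% | 13% |
| 58% | 0% | 31% |
| 60% | 0% | 46% |

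Now assume instead that true scores are uniform on 10-70%, and condition on a first score of 20-60%. Then P(R > 60) = 6.7% and P(R < 20 with a fall under 10 points) = 4.2%, together 10.9%, or about 11%. The trigger fires by chance in 7% if 10% means points and in 28% if it is relative, a ratio of 28/7 = 4.

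**The case against.** A reader might infer that the rule tests only the size of a fall, and so lets subjects outside the entry limits be implanted. The documents do not support that. Section 5.4 ties candidacy to the inclusion and exclusion criteria, and the Note says candidacy must be re-confirmed by the CNC retest. The natural standard for that is criteria 4 and 5. The 10% sentences can be read as deciding only what is repeated and which scores are analysed. Any observed change also goes to the sponsor, whose study manager assesses candidacy (Section 5.4.1.5). The CNC part is therefore an ambiguity.

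Nor does the 11% show subjects outside the intended population. It assumes no true change, and under the same model 47% of those out-of-range retests come from subjects whose true score lies within 20-60%. It applies only to late surgery, which the Note treats as an exception. If 1 to 5 of 10 subjects were late (an assumption), 0.11 × 1 to 0.11 × 5 is about 0.1 to 0.5 subjects.

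For objective 1, the protocol fixes no threshold-shift endpoint or reference audiogram, and these may be in an SAP. On-time subjects may also have audiograms up to 90 days old. Because both ears are tested after surgery, the other ear gives some indication of background progression. Bias is therefore possible but not shown.

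The audiogram gap survives all of this. Sponsor review covers changes that were observed, and an unmeasured threshold change is not among them. The other ear is only an indirect guide to the implanted one.

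**Conclusion.** The point holds in a limited form. For late surgery with a CNC fall below 10%, or a rise, criterion 2 is not rechecked on any reading, and the pre-operative audiogram can be more than 90 days old with no upper limit. This could blur objective 1 for those subjects. Its size is unknown, because the protocol gives neither the number of late surgeries nor a rate of threshold drift.

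The CNC part is a drafting ambiguity: whether a late retest must again meet criteria 4 and 5, what 10% means, and which ear it applies to. The figure of about 11% illustrates how often the ambiguity could matter per late-surgery subject. It rests on binomial scoring of 100 words, no true change, true scores uniform on 10-70%, and 10% read as points. It is not an estimate of ineligible implantations.

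**What to change.** 1. Repeat the unaided air-conduction audiogram at every late re-confirmation visit, whatever the CNC result. Name it as the pre-operative reference for hearing preservation, and add it to the Section 5.7 schedule.
2. Reconcile Section 4.1, Section 5.4, footnote 4 and the Section 5.4.2.2 Note so that they state whether late-retest CNC scores and thresholds must again meet Section 4.1, including after a rise. Which rule applies is for the sponsor and investigator to decide.
3. Define 10% as percentage points or as a relative fall, and name the ear or ears.

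The cost is protocol wording plus one short routine test, for late-surgery subjects only, at a visit that already takes place. If the sponsor decides that the limits apply again, some late candidates near them may become screen failures through test-retest noise alone. On the model above, about 12% of late subjects would retest outside 20-60% with no true change, counting low retests whether or not they reach the trigger. In a study of at most 10 subjects that should be weighed when item 2 is settled. Item 1 stands on its own, whatever is decided there.

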5.3.2 Consonant-Nucleus-Consonant (CNC) Word Recognition Test

The CNC Word Test (Peterson & Lehiste, 1962) is a validated test used clinically and in research to assess the performance of adults with hearing aids or cochlear implants on open-set word recognition. The test consists of 10 recorded lists of 50 monosyllabic words in CD format, tested in quiet. Two lists will be administered in at 60 dBA in the sound field and scored as total number of words correct, which will be expressed as a percentage correct for this study.

The AzBio Test (Spahr et al, 2012) is a validated test used clinically and in research to assess the open-set sentence recognition in speech-spectrum noise of adults with hearing aids or cochlear implants. It consists of 15 lists of 20 sentences each. AzBio sentences are spoken by different talkers in a conversational style with limited contextual cues that the listener can use to predict or 'fill in' unintelligible words. The sentences will be presented at a fixed level background noise and fixed signal-to-noise ratio. Each list includes 5 sentences from 4 different male and female speakers. Each word in the sentence counts towards the overall score. Subjects will be tested in noise at +5 dB SNR with speech at 0° and noise at 0° azimuth (S_0N_0) using multi-talker babble.

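### When CNC is retested because surgery is late, the retest result itself decides which implant-ear score becomes the analysis baseline

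*Protocol*

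**What the plan says.** The Note in Protocol 5.4.2.2 and footnote 4 to section 5.4 (printed under 5.4.1.1) give the same rule for late surgery. The Note starts it when the interval exceeds 3 months and asks for "repeating aided CNC word recognition test measures in quiet for each ear". Footnote 4 starts it "If it is more than 90 days past the date of the Candidacy Evaluation" and names no ear.

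The retest then leads to one of two branches:
- "If a patient experiences a 10% or greater decrement in their word recognition scores": thresholds are re-assessed, the Baseline Evaluation is repeated, and "Scores from the most recent test session will be used for analysis".
- With a smaller decrement, nothing need be repeated and "scores from the initial candidacy/ baseline assessment can be utilized". An unchanged or higher retest has no rule of its own and falls here.

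Implant-ear CNC is measured before surgery only at Candidacy (5.4.1.3: "Unilateral aided each ear with contralateral ear plugged") or at its retest. The Baseline Evaluation (5.4.2.1) has CNC in the bilateral aided condition only. Section 5.3.2 scores CNC as words correct, "which will be expressed as a percentage correct for this study".

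**The concern.** A baseline should be fixed before its value is known. Here a low retest must replace the first score, while a high retest need not. Nor does the repeated Baseline Evaluation supply a fresh implant-ear measurement, so regression to the mean is carried into the baseline. In the other branch the permissive wording leaves the choice open after both values have been seen.

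The baseline carries weight in this trial. Section 2.1 makes each subject their own control, and section 8.3 sorts subjects into better, unchanged or worse. With up to 10 subjects (section 4.0), one reclassified subject moves those proportions by 1/10, or 10 percentage points.

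The trigger is also loosely worded. Neither place says which ear's fall counts or whether 10% means percentage points.

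**Working it through.** The protocol gives no figure for this rule, no test-retest variability and no retest frequency, so there is nothing to reproduce. The rule can be evaluated under stated assumptions.

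**Inputs from the protocol.** Two lists of 50 words make 100 words per score (5.3.2). The implant-ear entry range is 20–60% (4.1). There are up to 10 subjects (4.0).

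**Assumptions.** Errors are binomial and independent between sessions, 10% means points, the implant ear is the trigger, and the first score is kept when the rule is not triggered.

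**Model.** First score X1 ~ Binomial(100, p). Retest X2 ~ Binomial(100, p − d/100), where d is the true decline in points. Baseline B = X2 if X1 − X2 ≥ 10, otherwise X1. Net error = E[B] − 100(p − d/100). All results are by exact enumeration.

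**Stable hearing, p = 0.4, no entry limits.** The SD of X1 − X2 is √(2 × 100 × 0.4 × 0.6) = 6.9 points, so a 10-point fall is not rare by chance. P(switch) = 0.0851 and the mean fall given a switch is 12.69. The mean shift is −0.0851 × 12.69 = −1.08 points. A switched subject's baseline lies on average 6.2 points below the truth.

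**Stable hearing, by true score** (net error in points):

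| True score | P(switch), no limits | Rule, no limits | Rule, 20–60% limit on first score | Latest score, limit on first score | Latest score, limit on both scores |
|---|---|---|---|---|---|
| 20% | 4.6% | −0.55 | +1.9 | 0 | +2.9 |
| 30% | 7.1% | −0.88 | −0.8 | 0 | near 0 |
| 40% | 8.5% | −1.08 | −1.1 | 0 | near 0 |
| 50% | 8.9% | −1.14 | −1.2 | 0 | near 0 |
| 60% | 8.5% | −1.08 | −3.7 | 0 | −3.6 |

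At 30–50% the rule's error is −0.7 to −1.2 however the entry limits are handled. At the ends, most of the error comes from admitting only first scores inside the limits. With the limit on the first score, it is about 0.0 at a true 25%.

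**Classification, p = 0.4, no device effect.** The cut-off of 10 points is mine, since section 8.3 sets none. Under the rule, 11.0% of retested subjects show a false gain and 5.9% a false loss. With the latest score the figures are 8.5% and 8.5%.

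**True decline, limit on first score only, true first score 30–50%.** Net error is about +0.1 to +0.6 at d = 2 and +1.1 to +1.6 at d = 4, because real falls below the threshold are ignored. The latest score gives 0.

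**Group level, p = 0.4, stable.** If 2 of 10 are retested, the group mean shifts by −1.08 × 2/10 = −0.2 points, and the chance of at least one switch is 1 − (1 − 0.0851)² = 16%. If 5 of 10, the shift is −0.5 and the chance 36%.

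**Effect of the loose wording, stable, no limits.** If 10% is read as relative to the first score, P(switch) is 18–36% and the shift −1.8 to −2.3. If a fall in either ear triggers (independent ears, same true score), P(switch) is 9–17%. If the permissive branch were used always to take the lower score, the shift would be −2.3 to −2.8.

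**The case against.** The strongest reply has four parts.

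- **Few or no subjects are affected.** Surgery is required within 3 months, and the retest applies only when that is missed. This stands: the affected group may be empty, no hypothesis is tested, and the group shift is small.
- **The direction is not established.** The rule exists to catch decline during a delay, and with decline of 2 points or more the error at 30–50% turns positive. This stands. A reader might infer that the rule systematically favours the device, but the documents do not say that hearing is stable over the delay, so that reading is unsupported.
- **The entry limits alter the figures.** This also stands. A chance-switch rate of 4.6–8.9% and a shift of about −0.5 to −1.1 should not be quoted for the whole 20–60% range, because they ignore selection on the first score, which dominates at both ends. Nor is the latest score free of error in every case: if the limits are re-applied to the retest, it is selected too.
- **The present rule keeps scores of one date together, changes are reviewed with the sponsor before surgery, and an unseen SAP could name the score in the permissive branch.** The first is a real advantage. The sponsor review does not say which score is the baseline. An SAP could settle the permissive branch, but the protocol itself already fixes the branch after a fall.

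**Conclusion.** The point holds as a minor one. The protocol makes the choice of implant-ear baseline depend on the retest value, and the replacement is the very score that triggered it. The size rests on the binomial model, the 10-point reading and the implant-ear trigger, and the figure of about 1 point too low for mid-range subjects also needs stable hearing. It does not support a claim of bias in one direction or of a material effect on the group result. The practical risk is one misclassified individual in section 8.3.

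The gap between 3 months and 90 days, the unspecified ear and the unit of the 10% are clarifications that would not justify a change alone.

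**What to change.** In both the Note in 5.4.2.2 and footnote 4, state that whenever CNC is repeated before surgery, the most recent implant-ear score is the analysis baseline, whatever the direction or size of the change. Leave the candidacy re-confirmation procedure as it is. While editing, reconcile 3 months with 90 days, and state which ear's fall counts and whether 10% means percentage points.

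The cost is wording only, since the retest is already required and no visit or list is added. There are two downsides:
- After a small change, a new implant-ear CNC is paired with older bilateral CNC, AzBio and questionnaire scores.
- If the 20–60% limits are re-applied to the retest, the gain near those limits is little or none (latest score about +2.9 at a true 20% and −3.6 at 60%, against near 0 at 30–50%, with stable hearing).
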